10.3.3.2. Pharmacodynamic Statistical Inference	54
10.3.4. Pharmacokinetic/Pharmacodynamic Analyses	54
10.3.5. Data Review During the Study	54
10.3.6. Interim Analyses	54
11. References	55
12. Appendices	58

List of Tables

Table		Page
Table GZKA.1.	Objectives and Endpoints	24
Table GZKA.2.	CCl	30
Table GZKA.3.	Treatments Administered.....	37

List of Figures

Figure		Page
Figure GZKA.1.	Illustration of study design for Part A.....	26
Figure GZKA.2.	Illustration of study design for Part B.....	27

List of Appendices

Appendix		Page
Appendix 1.	Abbreviations and Definitions	59
Appendix 2.	Clinical Laboratory Tests (Fasting)	62
Appendix 3.	Study Governance, Regulatory and Ethical Considerations	63
Appendix 4.	Hepatic Monitoring Tests for Treatment-Emergent Abnormality	66
Appendix 5.	Blood Sampling Summary	67
Appendix 6.	Excluded Concomitant Medications	69
Appendix 7.	Protocol Amendment J2M-MC-GZKA(c) Summary - A Safety, Tolerability, Pharmacokinetic, and Pharmacodynamic Study of Single- and Multiple-Ascending Doses of LY3478045 in Healthy Subjects	71

1. Protocol Synopsis

Title of Study:

A Safety, Tolerability, Pharmacokinetic, and Pharmacodynamic Study of Single- and Multiple-Ascending Doses of LY3478045 in Healthy Subjects.

Rationale:

Lilly is developing LY3478045, a ketohexokinase inhibitor, that helps in attenuation of fructose metabolism thus, anticipated to result in

- reduction of liver fat, inflammation, and fibrosis
- improvement in glycemic control
- insulin sensitization, and
- reduction in body weight, free fatty acids, and triglycerides.

Study J2M-MC-GZKA (GZKA) is a first-in-human study, which aims to assess the safety, tolerability, pharmacokinetics (PK), and pharmacodynamics (PD) of single and multiple oral doses of LY3478045 in healthy subjects. The PK, PD, safety, and tolerability data from this study in healthy subjects will assist in identifying an appropriate dose range for subsequent clinical studies in patients with nonalcoholic fatty liver disease and nonalcoholic steatohepatitis.

Objective(s)/Endpoints:

Objectives	Endpoints
Primary To investigate the safety and tolerability of single and multiple oral doses of LY3478045 in healthy subjects.	Incidence of TEAE and SAE. Clinically significant changes in vital signs data, safety laboratory parameters, and electrocardiograms.
Secondary To determine the pharmacokinetics of LY3478045 following single and multiple doses in healthy subjects.	AUC(0-24), AUC(0-inf), C _{max} , and t _{max} .

Abbreviations: AUC(0-24) = area under concentration versus time curve from time zero to 24 hours; AUC(0-inf) = AUC from time zero to infinity; C_{max} = maximum observed drug concentration; SAE = serious adverse event; t_{max} = time of C_{max}; TEAE = treatment-emergent adverse event.

Summary of Study Design:

Study GZKA is a Phase 1, single site, randomized, double-blind, placebo-controlled, 2-part study of LY3478045 in healthy subjects.

Part A: single-ascending dose.

Part B: multiple-ascending dose design that evaluates the potential for a drug-drug interaction.

In Part A, single-ascending oral doses of either LY3478045 or placebo will be administered in up to 5 cohorts. Each cohort will consist of at least 8 subjects, 6 subjects will receive LY3478045 and 2 subjects will receive placebo. Cohort 5 is an optional cohort that may be assessed based on the available safety and PK data from the previous 4 cohorts.

Part B will be initiated after assessing safety, tolerability, PK, and PD data through Cohort 3 in Part A.

Multiple-ascending oral doses of LY3478045 will be administered once daily for 14 days in up to 4 cohorts. Each cohort will consist of at least 8 subjects. In Cohorts 1 and 3, six subjects will receive LY3478045 and 2 subjects will receive placebo. In Cohorts 2 and 4, six subjects will receive LY3478045 followed by a single dose of **CC1** and 2 subjects will receive placebo followed by a single dose of atorvastatin **CC1** later.

Treatment Arms and Planned Duration for an Individual subject:

Treatment Name	LY3478045	Placebo	Atorvastatin
Dosage Formulation	CC1	Capsules	Tablets
Dose strength	CC1	-	40 mg
Route of Administration	Oral	Oral	Oral

The planned duration for each subject is approximately 43 days in Part A and 57 to 59 days in Part B of the study.

Number of Subjects:

Up to 50 subjects may be enrolled in Part A to ensure that at least 40 subjects complete the study (depending on whether subjects will be enrolled in optional Cohort 5). Up to 40 subjects may be enrolled in Part B to ensure that at least 32 subjects complete the study.

Statistical Analysis:

Pharmacokinetic/PD analyses will be conducted on data from all subjects who receive at least 1 dose of the investigational product and have evaluable PK and PD data. Safety analyses will be conducted for all enrolled subjects, whether or not they completed all protocol requirements. Additional exploratory analyses of the data may be conducted as deemed appropriate.

Safety parameters that will be assessed include clinical laboratory parameters, vital signs, and electrocardiogram parameters. Analyses may be performed to determine the effects of PK and PD parameters on QT interval corrected using Fridericia's formula.

The primary parameters for analysis will be maximum observed drug concentration (C_{max}), time of C_{max} (t_{max}), area under concentration versus time curve (AUC) from time zero to 24 hours (AUC0-24) and AUC from time zero to infinity (AUC0-inf) of LY3478045. The primary PK parameters for analysis of **CC1** will be AUC(0-inf) and C_{max} .

2. Schedule of Activities

Study schedules for Protocol J2M-MC-GZKA are presented for Part A (SAD; Section 2.1) and Part B (MAD; Section 2.2 [Cohorts 1 and 3]) and Section 2.3 [Cohorts 2 and 4 with atorvastatin]).

2.1. Part A (Single-Ascending Doses)

	Screening	Days							FU ^a	ED ^b	Comments
Procedure	^c ≤28 days before Day -1	-1	1	2	3	4	5	7	14		
Informed Consent	X										
Admission to CRU		X									
Discharge from CRU						X					Subjects may be discharged on Day 5 at the discretion of the investigator.
Non-Residential Visit							X	X	X	X	
LY3478045 Administration			X								
Medical History	X										Information regarding occasional use of vitamin/mineral supplements will be taken as a part of the medical history evaluation at the time of subject screening.
Complete Physical Examination	X								X	X	Targeted PE may be conducted at other visits at the discretion of the investigator.
Height	X										
Weight	X	X									
Pregnancy Test	X	X							X	X	Serum pregnancy test will be performed at screening and urine pregnancy test will be performed at all other specified timepoints.
Blood Pressure and Pulse Rate (Supine) ^c	X	X	P, every 1 h up to 12 h postdose	24, 36 h	48 h	72 h		X	X	X	
Body Temperature	X	X							X	X	
Clinical Laboratory Tests	X	X	P	X	X			X	X		See Appendix 2 for complete list.
Serum Creatinine ^d			P, 4, 12, 24 h								
TriPLICATE 12-Lead ECG			Predose: 1.5 h, 1 h, and 30 min. Postdose: 0.5, 1.5, 2.5, 4, 6, 8,	24 h							

	Screening	Days							FU ^a	ED ^b	Comments
Procedure	≤28 days before Day -1	-1	1	2	3	4	5	7	14		
			10, 12, 16 h								
Single 12-Lead ECG	X				X				X	X	
Adverse Event Recording	X	X	X	X	X	X	X	X	X	X	
Pharmacokinetic Sampling ^d			P, 0.75, 1.5, 3, 4, 6, 8, 10, 12, 16 h	24 h	48 h	72 h	96 h				
Meal (Low Fructose)			20 min, 6, 12 h								
Fructose Beverage (for Fructose Tolerance Test)			during meal: 20 min, 6, 12 h								
Fructose Tolerance Test Assay ^d			CCI	CCI							
Genetic Sample			X								
Fasting Biomarker Samples (Nonpharmacogenetic)		X		X							
CCI			P, 0.75, 1.5, 3, 4, 8, 12, 16 h	24 h	48 h	72 h	96 h				
24-hour Urine Collection for LY3478045 and Creatinine ^d			0-12, 12-24 h	24-36, 36-48 h	48-60, 60-72 h						

Abbreviations: CRU = clinical research unit; ECG = electrocardiogram; ED = early discontinuation; FU = follow-up; h = hour(s); min = minutes; P = predose; PE = physical examination.

Notes: If multiple procedures take place at the same time point, the following order of the procedures should be used: ECG, vital signs, and venipuncture. Samples collected for clinical laboratory tests including urine analysis may be analyzed at a local laboratory. All time points specified in the table are approximate and may be adjusted at the discretion of the investigator.

a Additional FU visits may occur depending upon emerging pharmacokinetic and/or safety data.

b At the discretion of the investigator, subjects may be requested to return to the CRU for safety monitoring at additional visits following completion of the ED procedures. At the discretion of the investigator, assessments may include, but will not be limited to, those presented for the FU visit with the addition of safety laboratory tests.

c Time points may be added for each study period, if warranted and agreed upon between Lilly and the investigator.

d Sampling times are relative to the time of study treatment administration (0 min).

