7.1. Treatment Administered

LY3478045 or placebo will be administered orally with approximately 240 mL of room temperature water in the morning of each dosing day (Day 1 in SAD; Days 1 to 14 in MAD) in a sitting position. Subjects will not be allowed to lie supine for 2 hours after dosing, unless clinically indicated or for study procedures.

Table GZKA.3. Treatments Administered

Treatment Name	LY3478045	Placebo	Atorvastatin
Dosage Formulation	CC1	Capsules	Tablets
Dose strength		-	40 mg
Route of Administration	Oral	Oral	Oral

The investigator or designee is responsible for

- explaining the correct use of the investigational product(s) to the site personnel
- verifying that instructions are followed properly
- maintaining accurate records of investigational product dispensing and collection, and
- returning all unused medications to Lilly or its designee at the end of the study

Note: In some cases, sites may destroy the material if, during the investigative site selection, the evaluator has verified and documented that the site has appropriate facilities and written procedures to dispose off the clinical materials.

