9.4.2.1. Vital Signs

For each subject, vital sign measurements should be conducted according to the Schedule of Activities (Section 2).

Blood pressure and pulse rate should be measured after at least 5 minutes supine.

If orthostatic measurements are required, subjects should be supine for at least 5 minutes and stand for at least 2 minutes.

If the subject feels unable to stand, supine vital signs only will be recorded.

Unscheduled orthostatic vital signs should be assessed, if possible, during any AE of dizziness or posture-induced symptoms. Additional vital signs may be measured during each study period if warranted.

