9.4.4. Body Temperature

Body temperature will be measured as specified in the Schedule of Activities (Section 2) and as clinically indicated.

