9.6.4 Vital signs

Vital signs data will be summarized by Part and treatment group together with changes from baseline, where baseline is defined as the Day 1 predose assessment. Figures of mean vital signs and mean changes from baseline profiles will be presented by Part and treatment.

Values for individual subjects will be listed.

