9.6.10 Other assessments

All other safety assessments not detailed in this section will be listed but not summarized or statistically analyzed.

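### No routine body temperature is scheduled between the first dose and follow-up, so for completers the planned readings cannot describe an acute or on-treatment temperature effect against placebo.

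*Protocol*

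**What the plan says.** **Schedule.** Protocol Sections 2.1 (Part A), 2.2 (Part B, Cohorts 1 and 3) and 2.3 (Part B, Cohorts 2 and 4) each carry a row "Body Temperature" marked four times: screening, Day -1, follow-up and early discontinuation. Follow-up is Day 14 in Part A and Day 28 in Part B.

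**Dosing.** Section 7.1 gives the dosing days as "Day 1 in SAD; Days 1 to 14 in MAD".

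**Unscheduled readings.** Section 9.4.4 states: "Body temperature will be measured as specified in the Schedule of Activities (Section 2) and as clinically indicated". The notes under the schedules add: "All time points specified in the table are approximate and may be adjusted at the discretion of the investigator".

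**Classification.** Section 9.4.2.1, Vital Signs, deals with blood pressure and pulse rate: "Blood pressure and pulse rate should be measured after at least 5 minutes supine". Temperature has its own Section 9.4.4, and Section 9.4.2 groups it with routine medical assessments.

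**Analysis.** SAP 9.6.4 summarises vital signs and their changes, "where baseline is defined as the Day 1 predose assessment", without naming the parameters. The SAP does not mention body temperature. Its catch-all, 9.6.10, reads: "All other safety assessments not detailed in this section will be listed but not summarized or statistically analyzed".

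**The concern.** This is a first-in-human study, and its protocol sets out to collect temperature. It collects it routinely only before the first dose and about two weeks after the last one. Any rise or fall while the drug is acting would be recorded only if a subject discontinued at that time or someone saw a reason to measure. Readings triggered in that way are not taken at the same times in active and placebo subjects, so they cannot be set against each other.

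Two features of the protocol give this some weight. First, under Section 7.4.1, escalation draws on clinical assessment through Day 7, and under Sections 5.1.1 and 5.1.2 the rest of a sentinel cohort may be dosed from 48 hours. The first routine post-dose temperature comes later than both. Second, the hepatic criteria in Section 8.1, which apply in Part B, list fever among the features considered together with raised liver enzymes. Laboratory tests are scheduled during dosing, but temperature is not.

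The SAP leaves a smaller gap. A programmer cannot tell whether temperature belongs with vital signs, where the stated baseline is a Day 1 predose value that is not scheduled for it, or is only listed.

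**Working it through.** **1. Confirm the follow-up days.** The synopsis says: "The planned duration for each subject is approximately 43 days in Part A and 57 to 59 days in Part B of the study". Adding the screening window, the days before dosing and the follow-up day reproduces this:

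- Part A: 28 + 1 + 14 = 43 days.
- Part B, Cohorts 1 and 3: 28 + 1 + 28 = 57 days.
- Part B, Cohorts 2 and 4: 28 + 3 + 28 = 59 days.

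Follow-up on Day 14 and Day 28 is therefore the right reading.

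**2. Interval from last dose to first routine post-dose temperature (completers).** Interval = follow-up day − last dosing day.

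- Part A: 14 − 1 = 13 days.
- Part B: 28 − 14 = 14 days.

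**3. Count of routine readings.**

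| | Part A | Part B |
|---|---|---|
| Day -1 | 1 | 1 |
| Day 1 predose | 0 | 0 |
| After first dose, before follow-up | 0 | 0 |
| Follow-up | 1 | 1 |

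**4. Comparison with blood pressure and pulse.** Day 1 has predose plus 12 hourly times: 1 + 12 = 13. In Part A the post-dose times before follow-up are the 12 hourly ones, then 24, 36, 48 and 72 h, and Day 7: 12 + 4 + 1 = 17. The corresponding number for temperature is 0.

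**5. SAP baseline, under each classification.**

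- If temperature is a vital sign under 9.6.4, the baseline is Day 1 predose, and no such reading is scheduled. A Day -1 reading exists in every cohort.
- If temperature falls under 9.6.10, it is listed only and needs no baseline.
- Precedent: SAP 9.6.7 gives body weight, which also has no Day 1 value, its own baseline of Day -1 (Cohorts 1 and 3) or Day -3 (Cohorts 2 and 4).

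**Reading of the tables.** The text of the schedules in 2.2 and 2.3 is broken in extraction. Columns were matched against neighbouring rows such as weight and physical examination. The Day 14 blood pressure mark is clear in 2.2; in 2.3 its column has shifted and should be checked against the original table.

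**The case against.** The strongest case against has four parts.

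- **Temperature need not be a vital sign.** The protocol's vital-signs section covers blood pressure and pulse, temperature sits in its own section, and SAP 9.6.10 provides for listing. This stands. A reader might infer that the SAP contradicts itself, or that temperature belongs to the primary endpoint because that endpoint includes clinically significant vital-sign changes. Neither document says so. The SAP point is an ambiguity, not an error.
- **The data are not worthless.** A reader might infer that the temperature data cannot show any drug effect. That goes too far. A change from Day -1 to follow-up against placebo could show a persisting effect, and early-discontinuation or clinically indicated readings can fall on treatment. The follow-up visit cannot be called drug-free with certainty either, since the PK projections are redacted. This also stands.
- **Fever would be noticed.** Adverse events are recorded throughout, subjects are resident on every dosing day, and the investigator may measure at any time without waiting for a complaint. This holds for clinically apparent fever. It does not supply readings at matched times in both arms, and permission to adjust time points does not prespecify any.
- **No signal calls for it.** Section 3.3 anticipates no risk from target inhibition. Much of the nonclinical material is redacted, so the need for on-treatment temperature cannot be judged from the public text. That limits how strongly the change can be urged. It does not remove the case for a nearly free measurement.

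**Conclusion.** For completers, the plan has no routine temperature from first dose to follow-up: none on the single dosing day and none in the next 12 days in Part A, and none on any of the 14 dosing days in Part B. The first routine post-dose reading is 13 or 14 days after the last dose. The planned data therefore cannot describe an acute or on-treatment effect on temperature against placebo. That is the full extent of the finding.

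It rests on the column positions of the temperature marks, which agree across the three schedules, and on the follow-up days, which agree with the stated study durations. It does not depend on temperature being a vital sign.

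This is a modest, inexpensive improvement, not a flaw in the primary analysis. Any resulting comparison would be descriptive: with 6 active and 2 placebo subjects per cohort, pooled placebo would number 5 × 2 = 10 in Part A and 4 × 2 = 8 in Part B if every planned cohort is run.

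**What to change.** **Protocol, Sections 2.1 to 2.3.** Add body temperature at Day 1 predose and at a few post-dose blood pressure times already in the schedule: for example, one within the 12 h profile on Day 1, the 24 h time, and Day 14 in Part B. In that example, Part A gains three readings per subject and Part B four.

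**SAP (minor clarification).** State one of two things:

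- temperature is summarised with vital signs under 9.6.4, with Day 1 predose as baseline, or Day -1 where no Day 1 value exists, much as 9.6.7 does for weight; or
- temperature is listed only, under 9.6.10.

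**Cost.** A few seconds per time point, at moments when staff are already taking blood pressure, and one line in the SAP. No blood draw and no extra visit.

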2.2. Part B (Cohorts 1 and 3; Multiple-Ascending Doses)

Procedure	Screening	Days										FU ^a	ED ^b	Comments
		-1	1	2	3 to 6	7	8	9 to 13	14	15 to 17	28			
Informed Consent	X													
Admission to CRU ^c		X												
Discharge from CRU											Day 17			
LY3478045 Administration						X								
Medical History	X													Information regarding occasional use of vitamin/mineral supplements will be taken as a part of the medical history evaluation at the time of subject screening.
Complete Physical Examination	X											X	X	Targeted PE may be conducted at other visits at the discretion of the investigator.
Height	X													
Weight	X	X									Day 15	X	X	
Pregnancy Test	X	X										X	X	Serum pregnancy test will be performed at screening and urine pregnancy test will be performed at all other specified

	Screening	Days										FU ^a	ED ^b	Comments
Procedure	≤28 days before Day -1	-1	1	2	3 to 6	7	8	9 to 13	14	15 to 17	28			
														timepoints.
Blood Pressure and Pulse Rate (Supine) ^c	X	X	P, every 1 h up to 12 h postdose	24, 36 h	48, 72 h				X		X	X		
Body Temperature	X	X										X	X	
Clinical Laboratory Tests (See Appendix 2)	X	X	P		Day 4	X			X		X	X		
Serum Creatinine			X			X			X					
Total Testosterone, Follicle-Stimulating Hormone, and Luteinizing Hormone	X		P	P							X	X	Samples will be collected early in the morning on Days 1 and 2, at the same time for both days, before or immediately after breakfast.	
Single 12-Lead ECG	X										X	X		
TriPLICATE 12-Lead ECG			Predose: 1.5 h, 1 h, and 30 min.						P, 0.5, 1.5, 2.5, 4, 6, 8, 12, 16 h	24 h				
Adverse Event Recording	X	X	X	X	X	X	X	X	X	X	X	X		
Pharmacokinetic Sampling ^d			P, 0.75, 1.5, 3, 4, 6, 8, 12, 16 h	24 h (predose)		P			P, 0.75, 1.5, 3, 4, 6, 8, 12, 16 h	24, 48, 72 h			Sampling times may be adjusted based upon review of interim PK	
Fasting Insulin and Adiponectin			P						P					
Meal (Low Fructose)			20 min, 6 h, 12 h						20 min, 6 h, 12 h					

Procedure	Screening ≤28 days before Day -1	Days										FU ^a	ED ^b	Comments
		-1	1	2	3 to 6	7	8	9 to 13	14	15 to 17	28			
Fructose Beverage (for Fructose Tolerance Test)			during meal: 20 min, 6, 12 h						during meal: 20 min, 6, 12 h					
Fructose Tolerance Test Assay ^d			CCI	CCI					CCI	CCI				
Genetic Sample		P												
Fasting Biomarker Samples (Nonpharmacogenetic)		X		X							Day 15			
CCI			P, 1,5, 3, 4, 6, 8, 12, 16 h	24 h (predose)		P, 1,5, 3, 4, 6, 8, 12, 16 h	24 h (predose)							Sampling times may be adjusted based upon review of preliminary data

Abbreviations: CRU = clinical research unit; ECG = electrocardiogram; ED = early discontinuation; FU = follow-up; h = hour(s); min = minutes; P = predose; PE = physical examination; PK = pharmacokinetics.

Notes: If multiple procedures take place at the same time point, the following order of the procedures should be used: ECG, vital signs, and venipuncture. Samples collected for clinical laboratory tests including urine analysis may be analyzed at a local laboratory. All time points specified in the table are approximate and may be adjusted at the discretion of the investigator.

- a Additional FU visits may occur depending upon emerging pharmacokinetic and/or safety data.
- b At the discretion of the investigator, subjects may be requested to return to the CRU for safety monitoring at additional visits following completion of the ED procedures. At the discretion of the investigator, assessments may include, but will not be limited to, those presented for the FU visit with the addition of safety laboratory tests.
- c Where possible, measurements of blood pressure and pulse rate should be performed at approximately the same time of day at each scheduled time point. Time points may be added for each study period, if warranted and agreed upon between Lilly and the investigator.
- d Sampling times are relative to the time of study treatment administration (0 min).
- e If the predicted mean exposure for the dose at any cohort is estimated to be higher than 71.7 µg·hr/mL, only female subjects will be included in the cohort and mandated to stay in the CRU until 24 hours after the last dose.

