3.3. Benefit/Risk Assessment

LY3478045 has not been administered to humans previously.

Given that there are no significant adverse events (AEs) in subjects who have a genetic deficiency for KHK (essential fructosuria), there are no anticipated risks based on target

inhibition. Further, the nonclinical pharmacology does not predict mechanism of action-based risk for this compound.

Study GZKA will be conducted in accordance with principles outlined in the Guideline on Strategies to Identify and Mitigate Risks for First-in-Human Clinical Trials with Investigational Medicinal Products (EMA 2017). Based on the nonclinical data, LY3478045 is not considered to be a high uncertainty compound.

There is no anticipated therapeutic benefit for the healthy subjects participating in this study.

The available nonclinical safety information for LY3478045 supports its evaluation in healthy subjects.

CCI

In recognition of the apparent steep dose-response curve in rats between the repeat-dose NOAEL in the 1-month GLP study and a nontolerated dose in a 14-day non-GLP study that was associated with mortality, sentinel dosing will be performed in Cohorts 3, 4, and 5 of Part A, as drug exposures in these dose cohorts are projected to approach 10-fold below the exposure observed at the NOAEL (CCI in dogs).

Overall, the nonclinical safety assessment risks identified for the planned doses in the current study are considered low.

More details about the known and expected benefits, risks, serious adverse events (SAEs), and reasonably anticipated AEs of LY3478045 is available in the Investigator's Brochure (IB).

4. Objectives and Endpoints

Table GZKA.1 shows the objectives and endpoints of the study.

Table GZKA.1. Objectives and Endpoints

Objectives	Endpoints
Primary To investigate the safety and tolerability of single and multiple oral doses of LY3478045 in healthy subjects.	Incidence of TEAE and SAE. Clinically significant changes in vital signs data, safety laboratory parameters, and electrocardiograms.
Secondary To determine the pharmacokinetics of LY3478045 following single and multiple doses in healthy subjects.	AUC(0-24), AUC(0-inf), C _{max} , and t _{max} .
Exploratory To determine the pharmacodynamic effects of LY3478045 following single and multiple doses in healthy subjects.	AUC(0-24) of fructose concentration over time following fructose tolerance test.

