5.1.2. Part B

Part B will be initiated after assessing safety, tolerability, PK, and PD data through Cohort 3 in Part A.

[figure not shown]
Multiple-ascending oral doses of LY3478045 will be administered once daily for 14 days in up to 4 cohorts. Each cohort will consist of 8 subjects. In Cohorts 1 and 3, six subjects will receive LY3478045 and 2 subjects will receive placebo. In Cohorts 2 and 4, six subjects will receive LY3478045 followed by a single dose of atorvastatin 4 hours later and 2 subjects will receive placebo followed by a single dose of atorvastatin 4 hours later.

The maximum dose in males and females in the MAD will be determined based on the PK analyses from previous cohorts, to ensure that the predicted mean exposure at steady state (AUC₀₋₂₄) at the maximum dose in males does not exceed CCI

CCI

A sentinel dosing strategy will be utilized in the cohorts for which the mean AUC₀₋₂₄ is predicted to exceed CCI. Two subjects (1 LY3478045 and 1 placebo) in the cohorts for which the mean AUC₀₋₂₄ is predicted to exceed CCI will receive a sentinel dose on the same day. At least 48 hours after dose, the remaining subjects in each cohort may be dosed based on the available safety data.

Figure GZKA.2 illustrates the study design.

Abbreviations: AT = atorvastatin; LY = LY3478045; PL = placebo.

Figure GZKA.2. Illustration of study design for Part B.

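### Part B schedules no timed blood pressure reading 1 to 11 h after any of doses 2 to 14, although vital-sign change after multiple doses is part of the primary endpoint

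*Protocol*

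**What the plan says.** The primary objective (Protocol Section 4, Table GZKA.1) covers single and multiple doses. One of its endpoints is "Clinically significant changes in vital signs data, safety laboratory parameters, and electrocardiograms". In Part B, doses "will be administered once daily for 14 days in up to 4 cohorts" (Protocol 5.1.2).

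Schedule 2.2 sets blood pressure and pulse at "P, every 1 h up to 12 h postdose" on Day 1, at 24 and 36 h on Day 2, and at 48 and 72 h in the Days 3 to 6 column. Days 7, 8 and 9 to 13 are blank. Day 14 has one mark with no clock time. The next entries are the Day 28 follow-up and early discontinuation.

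On Day 14 the same subjects have triplicate ECGs at "P, 0.5, 1.5, 2.5, 4, 6, 8, 12, 16 h" and PK samples at "P, 0.75, 1.5, 3, 4, 6, 8, 12, 16 h", with further timed samples afterwards.

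The footnote to the blood pressure row adds: "Time points may be added for each study period, if warranted and agreed upon between Lilly and the investigator". Protocol 9.4.2.1 likewise allows additional vital signs if warranted.

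SAP 9.6.4 takes Day 1 predose as baseline and promises: "Figures of mean vital signs and mean changes from baseline profiles will be presented by Part and treatment". It sets no time points of its own.

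**The concern.** The dense blood pressure profile sits at the first dose, and Part A already profiles single doses hourly. Part B exists to show what repeated dosing adds. A blood pressure change that builds with accumulation, and is largest in the hours after dosing, would fall where nothing timed is scheduled. The Part B figures under SAP 9.6.4 would show a detailed first-dose curve, a few points to 72 h, and then one Day 14 value whose relation to the dose is unknown.

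Dose escalation is affected too. Protocol 7.4.1 requires clinical assessment through Day 7 in at least 6 of 8 subjects. In Schedule 2.2, safety laboratory tests are due on Day 7, but the last scheduled blood pressure before then is at 72 h.

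**Working it through.** The plan states no figure to reproduce. The check is a count from Schedule 2.2, followed by an illustration of accumulation.

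**Alignment.** The adverse-event row fills every column of Schedule 2.2. The laboratory row has its late marks on Days 7, 14 and 28 and at early discontinuation. Set against these, the late blood pressure mark falls on Day 14.

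**Count of on-treatment postbaseline readings.** 12 (hourly, Day 1) + 2 (24, 36 h) + 2 (48, 72 h) + 1 (Day 14) = 17. Of these, 12 + 2 + 2 = 16 lie within 72 h of dose 1.

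**Hours after the most recent dose**, with doses at 0, 24, 48 h and so on, and readings at a dosing time taken as predose (the PK row labels its 24 h sample that way):

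| Reading | Most recent dose | Hours after it |
|---|---|---|
| 1 to 12 h | dose 1 | 1 to 12 |
| 24 h | dose 1 | 24 (trough) |
| 36 h | dose 2 | 12 |
| 48 h | dose 2 | 24 (trough) |
| 72 h | dose 3 | 24 (trough) |
| Day 14 mark | dose 13 or 14 | not stated |

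Timed readings 1 to 11 h after any of doses 2 to 14: **0**. Scheduled readings on Days 5 to 13: **0**, over 9 consecutive dosing days.

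**Cohorts 2 and 4.** Schedule 2.3 shows the same entries to 72 h, then one untimed mark late in or just after dosing. Its row has two late marks against three in Schedule 2.2, and the extracted columns do not align well enough to fix the day. The 16-of-17 count is therefore for Schedule 2.2 only.

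**Accumulation.** Half-life is not given, so a range is assumed, with linear kinetics. The fraction of steady-state exposure reached at dose n is 1 − 2^(−24n/t½). Steady-state accumulation is 1/(1 − 2^(−24/t½)).

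| Assumed t½ | Dose 1 | Dose 2 | Dose 3 | Accumulation |
|---|---|---|---|---|
| 6 h | 94% | 99.6% | >99.9% | 1.07 |
| 12 h | 75% | 94% | 98% | 1.33 |
| 24 h | 50% | 75% | 87.5% | 2.00 |
| 48 h | 29% | 50% | 65% | 3.41 |

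At 6 h, the hourly Day 1 profile is already close to steady state and the accumulation argument nearly disappears. At 24 h it is made at half of steady-state exposure, and at 48 h at less than a third.

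**The case against.** - **Repeat-dose blood pressure is measured.** The 36, 48 and 72 h readings follow doses 2 and 3. With a 12 h half-life those doses reach 94% and 98% of steady state; if tmax were near 12 h, the 36 h reading would even be near peak after dose 2. This stands. It limits the gap to the early postdose hours from dose 2 onward, and to the second week of dosing.
- **Readings can be added, and subjects are watched.** Subjects stay in the unit to Day 17 with continuous adverse-event recording. Safety data are reviewed after each dosing session, and orthostatic readings are called for, if possible, when dizziness occurs. A reader might infer from the schedule that the trial cannot detect a repeat-dose effect. The documents do not support that: readings may be added, and the Day 14 mark could fall near peak. But additions need a reason first, and a change without symptoms gives none.
- **ECG heart rate covers pulse.** It does on Day 14. It does not cover blood pressure.
- **The tables are damaged.** Daily dosing appears in Schedule 2.2 as a single mark, so merged cells have been lost. If the Day 14 mark once spanned several days, the statement about Days 5 to 13 would weaken. The mark would still have no time, so the zero count for 1 to 11 h would stand.
- **No blood pressure liability is identified.** The visible text names none, and the preclinical section and exposure table are redacted. ECGs also serve a planned concentration-response analysis that blood pressure lacks. This is a fair reason to treat the point as an improvement to the design, not a defect that undermines the trial.

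**Conclusion.** The point holds in a limited form. In Schedule 2.2, no timed blood pressure reading is scheduled 1 to 11 h after any of doses 2 to 14, and none at all on Days 5 to 13. A multiple-dose conclusion on this part of the primary endpoint would rest on trough readings to 72 h, one reading 12 h after dose 2, and one untimed Day 14 value per subject. Schedule 2.3 looks the same early on, with its late mark uncertain.

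The counts need no pharmacokinetic assumption beyond once-daily dosing. Their importance does: it is small if half-life is near 6 h and substantial at 24 h or longer, and it also depends on tmax. Neither value is given. The point concerns what is scheduled. It does not show that an effect exists or that one would necessarily be missed. The change is worth making because Day 14 already carries timed ECG and PK profiles in resident subjects.

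**What to change.** - **Schedules 2.2 and 2.3:** replace the untimed late mark with supine blood pressure and pulse at the existing Day 14 triplicate ECG times: predose, 0.5, 1.5, 2.5, 4, 6, 8, 12, 16 and 24 h (the last on Day 15). Subjects are already supine for the ECG, and the protocol's order is ECG, then vital signs.
- **Both schedules:** add one predose reading on Day 7, so that the assessment used for escalation includes a blood pressure.
- **Keep the Day 1 hourly series.** Thinning it to save effort would remove first-dose readings in a first-in-human study and would not pay for the additions: using the ECG times leaves 8 readings up to 12 h or later in place of 12, a saving of 4.
- **SAP 9.6.4:** present Day 14 change from Day 1 predose by nominal time and treatment, including placebo. The baseline and the summary by treatment are already there; only the Day 14 time axis is new.

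Cost: 10 readings in place of 1 is +9, and Day 7 makes +10 cuff readings per subject, all on days already resident, with no added visits or blood.
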